19	Supplement/Appendices.....	45

AE	Adverse Event/Adverse Experience
CFR	Code of Federal Regulations
CIOMS	Council for International Organizations of Medical Sciences
CRF	Case Report Form
DMID	Division of Microbiology and Infectious Diseases
DSMB	Data and Safety Monitoring Board
FWA	Federalwide Assurance
GCP	Good Clinical Practice
ICF	Informed Consent Form
ICH	International Conference on Harmonisation
IEC	Independent or Institutional Ethics Committee
IRB	Institutional Review Board
JAMA	Journal of the American Medical Association
MOP	Manual of Procedures
N	Number (typically refers to participants)
NEJM	New England Journal of Medicine
NIAID	National Institute of Allergy and Infectious Diseases, NIH, DHHS
NIH	National Institutes of Health
OCRA	Office of Clinical Research Affairs, DMID, NIAID, NIH, DHHS
OHRP	Office for Human Research Protections
ORA	Office of Regulatory Affairs, DMID, NIAID, NIH, DHHS
PI	Principal Investigator
SAE	Serious Adverse Event/Serious Adverse Experience
SMC	Safety Monitoring Committee
SOP	Standard Operating Procedure
WHO	World Health Organization

1 PROTOCOL SUMMARY

- Title:** A comparison of CD4 T cell induction and antibody responses between a pure hemagglutinin influenza vaccine (rHA, Protein Sciences Corp) and licensed subvirion influenza vaccine made in eggs (Sanofi) or cell culture (Novartis) in healthy adults.
- Population:** Healthy adults ages 18 to 49 years
- Number of Sites:** Single site study
- Study Duration:** 7 years
- Subject Duration:** 6 months
- Agents:** Flublok (baculovirus expressed HA), Flucelvax (inactivated vaccine generated in mammalian cell culture, Fluzone SD (inactivated vaccine generated in eggs, administered at 15 ug per HA), Fluzone HD (inactivated vaccine generated in eggs, administered at 60 ug per HA)

Primary Objective

- Comparison of the serum antibody response to immunization with pure HA, cell- derived and egg derived subvirion vaccines in adults age 18-49 years
- Comparison of the HA- specific CD4 T cell response in adults receiving pure HA, cell-derived or egg-derived split or subvirion vaccines

Secondary Objectives

- Comparison of the epitope specificity of B cells following vaccination with HA or subvirion vaccines

[figure not shown]
Evaluation of the different vaccine formulations to induce HA specific antibodies that recognize circulating viruses

Tertiary Objective

- Confirmation of the safety of the licensed vaccines in healthy adults
-
- Evaluation of the effect of repeated vaccination on the immune response

Schematic of Study Design:

Because it is possible that prior exposure will impact the relative impact of peptide specific help on the antibody response, subjects will be screened for pre-vaccination antibody. Subjects will be divided into relatively high (greater than 1:8) or low (equal to or less than 1:8) pre-vaccination antibody based on pH1N1. The basic study design for the healthy adults age 18-49 years is described below. Subjects will be queried regarding prior history of influenza vaccination, and stratified into those who have not been vaccinated in the previous year and those who have, followed by randomized assignment to receive one of four licensed vaccines. Study subjects who participated in a previous year can be re-enrolled and will receive the same vaccine they received previously. Because the goal of the protocol is to evaluate the immune response to the vaccine and is not intended as a formal comparison of the adverse event profile, the vaccine assignment is not blinded. Following vaccination, subjects will have samples of blood obtained at the time points illustrated above. The last study visit will take place approximately 6 months after vaccination in order to test the durability of the response.

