3 BACKGROUND INFORMATION AND SCIENTIFIC RATIONALE

3.1 Background Information

Inactivated influenza vaccines (IIVs) have been in use in the US and worldwide for the prevention of illness due to seasonal and pandemic influenza since their licensure approximately 60 years ago. Multiple studies over many years have evaluated the immunogenicity of these vaccines in various populations. In general, serum antibody responses to IIV are vigorous in healthy young adults with low levels of pre-vaccination antibody. Nasal antibody responses can also be detected, although they are not as vigorous as those seen after live vaccination.

The serum antibody response to IIV is impacted by several factors, including the age of the subject, the presence of chronic diseases, and the use of immune modulating drugs. In addition, the prior exposure of the subject to influenza vaccine or infection appears to have a substantial impact on both the immune response as well as the protective efficacy of IIV. For seasonal influenza vaccine, the magnitude of the serum antibody response is lower in individuals who begin with higher prevaccination titers, and highest in those with low prevaccination titers. Consistent with this observation, individuals with prior vaccination, and who therefore have higher baseline antibody titers, tend to have less vigorous antibody responses to revaccination. The impact of prior vaccination on protection is controversial. Some studies have suggested that vaccine efficacy is higher in those who were not vaccinated in the previous season than in those who were [1, 2]. Other studies have not seen this association [3]. The mechanisms by which prior exposure to vaccine or infection might modify the subsequent response to IIV are not known, but would have obvious implications for the design of new influenza vaccines and vaccine strategies.

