4.2 Outcome Measures

4.2.1 Primary Outcome Measures

The primary outcome measure for this study is:

- Mean change in the specificity, quantity and quality of serum antibody titers to the vaccine viruses, pH1N1, H3 and influenza B using HAI (year 1-5) and MN for pH1N1 and H3 viruses (years 1-5 from Day 0 to Day 28)

- Mean change in the CD4 T cell reactivity to pools of total pHA peptides derived from the pH1N1 HA, as well as H3, influenza B HA, NP, and M1 peptides will be quantified using cytokine Elispot From Day 0 to Day 14

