9.2 Laboratory Evaluations/Assays

9.2.1 Immunogenicity Evaluations

Serum hemagglutination-inhibition (HAI). HAI will be performed in microtiter format using turkey RBCs and egg-grown, betapropiolactone-inactivated A/California/07/09 virus as antigen. The titer of antibody will be defined as the highest dilution resulting in complete inhibition of hemagglutination. Sera will be treated with receptor-destroying enzyme and heat inactivated prior to testing at an initial starting dilution of 1:4. Sera with no detectable HAI titer will be assigned a titer of 1:2 for calculation purposes.

Microneutralization (MN) assay: Sera will be tested by microtiter technique for neutralization of an A/California/07/09 x PR8 reassortant virus in MDCK cells. Viral growth will be determined by ELISA of the cells following fixation with methanol using a combination of M- and NP-specific monoclonal antibodies. The titer of antibody will be defined as the highest titer resulting in 50% inhibition of antigen signal compared to un-neutralized control wells. Sera will be treated with RDE and heat inactivated prior to testing at an initial starting dilution of 1:10. Sera with no neutralizing titer will be assigned a value of 1:5 for calculation purposes.

B cell responses: Peripheral Blood Mononuclear Cells (PBMC) will be obtained before and on day 7 and 28 after vaccine and evaluated for B-cell responses. B cell responses will be evaluated by memory cell assay [16] and antibody secreting cell assay. In addition, B cells will be cultured in vitro and the functional quality of secreted antibody assessed by HAI and MN assays

CD4 T cell responses: PBMCs collected prior to and on day 3, 7, 14 and 180 after vaccination will be evaluated for the presence of antigen specific CD4 cells by ELISPOT assay and flow cytometry using a panel of peptides spanning the H1 hemagglutinin, neuraminidase and internal virion proteins such as NP and M1 [17]. This assay will identify both cross reactive and H1 specific epitope responses, as well as recall of memory cells to conserved internal virion proteins. PBMC will also be evaluated for the presence of antigen specific ELISPOT and cell homing markers by flow cytometry.

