12.4 Final Analysis Plan

We will define the groups as: G1 (egg derived vaccine) = G1a (seronegative to pH1N1 virus and receiving egg derived vaccine) + G1b (seropositive and receiving egg derived vaccine); G2 (baculovirus derived vaccine) = G2a (seronegative to to pH1N1 virus and receiving baculovirus derived vaccine) + G2b (seropositive and receiving baculovirus derived vaccine). The log transformation will be applied to stabilize variance, as suggested by our past experience [18]. The between-group and among-group comparison in each of the outcomes will be based on both standard statistical analysis approaches using summary statistics and the complicated random variance model approach. Specifically, each of CD4 specific cells for different Influenza proteins (eg HA, NP etc), memory B cell derived polyclonal antibodies, HAI and MN titers among the four groups and between G1 and G2, between G1a and G2a, and between G1b and G2b, we will use maximum responses or maximum boost responses (maximum value after day 0 – value at day 0) or maximum fold increase as endpoint and do group comparison by ANOVA for among-group comparison and two-sample t-test for between-group comparison, or their nonparametric analogy of Kruskal-Wallis test and Wilcoxon Rank sum test, respectively, may also be applied for robustness. Multiple comparisons may subject to Bonferroni correction, if appropriate. Correlation test such as Pearson correlation analysis, or its nonparametric analogy of Spearman correlation analysis, will be used to study how baseline CD4 responses and/or memory B cell derived polyclonal antibodies, HAI, MN titers affect the boost responses of CD4, memory B cell derived polyclonal antibodies, HAI and MN titers after vaccination.

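### Section 12.4 forms its prior-immunity subgroups on pH1N1 status alone and uses them for H3, influenza B and non-H1 CD4 outcomes, where they do not describe prior immunity to the virus analysed

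*Combined protocol and SAP*

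**What the plan says.** Section 1 (text under the study design schematic) gives the reason for the split: earlier exposure may alter how peptide-specific help affects the antibody response. The rule is then "Subjects will be divided into relatively high (greater than 1:8) or low (equal to or less than 1:8) pre-vaccination antibody based on pH1N1". The same paragraph also describes stratification by vaccination in the previous year.

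Section 12.4 defines the egg-derived group as "G1a (seronegative to pH1N1 virus and receiving egg derived vaccine) + G1b (seropositive and receiving egg derived vaccine"), and the baculovirus group in the same way. It gives no titre cut-off. The comparisons are of each CD4 specificity, memory B cell derived antibody, and "HAI and MN titers among the four groups and between G1 and G2, between G1a and G2a, and between G1b and G2b". No outcome is exempted and no virus-specific stratum is defined.

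Section 4.2.1 sets the primary antibody outcome as the change in titres "to the vaccine viruses, pH1N1, H3 and influenza B using HAI (year 1-5) and MN for pH1N1 and H3 viruses". The primary CD4 outcome covers H3, B HA, NP and M1 peptides as well as pH1N1 HA.

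Section 3.1 says that for seasonal vaccine "the magnitude of the serum antibody response is lower in individuals who begin with higher prevaccination titers".

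Section 3.2 reports that significant numbers of subjects with pH1N1 titres of 1:8 or less could not be found in the first full year. It therefore replaced that screen with randomization stratified by vaccination history. Section 5 describes only the vaccination-history strata.

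**The concern.** The split is there to ask whether the vaccine difference depends on prior immunity. For a pH1N1 titre, the pH1N1 baseline is the natural way to ask it. For an H3 or B titre, the natural modifier is the subject's own baseline to that virus. A pH1N1 label need not track it.

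Suppose a vaccine difference in H3 response exists only in subjects low to H3. It would then be diluted in G1a versus G2a, because some of those subjects are not low to H3. It would also spill into G1b versus G2b, because some H3-low subjects are classed there. Similar results in the two strata could be misread as showing that prior immunity to H3 does not matter. H3 is a live question here, since Section 3.2 closes the Flucelvax arm to new subjects because of its poor H3 immunogenicity.

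The subgroup is also not defined consistently. Two analysts working from Section 1 and Section 12.4 could assign the same subject to different strata.

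**Working it through.** **1. Does the pH1N1 split reach H3 and B?** Section 12.4 names no virus when it lists HAI and MN titres. Section 4.2.1 says which titres those are: HAI for pH1N1, H3 and B, and MN for pH1N1 and H3. Read together, the split applies to H3 and B HAI and to H3 MN. For CD4 cells, Section 12.4 itself names proteins other than HA. The reach to H3 and B titres is therefore an inference, but the plain one.

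**2. Is the subgroup the same in both sections?** Section 9.2.1 starts HAI at 1:4 and assigns 1:2 to sera with no detectable titre.

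| Day 0 HAI titre | Section 1 | Section 12.4 |
|---|---|---|
| 1:2 (undetectable) | low | seronegative |
| 1:4, 1:8 (detectable) | low | not determined; seropositive if the word means detectable |
| above 1:8 | high | seropositive |

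The sections agree only at the two ends.

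**3. How large could the mismatch be?** The plan has no figure to reproduce. Its only power statement (Section 12.2) concerns HA-specific CD4 counts in whole groups. No section reports baseline H3 or B titres or their relation to pH1N1 titres, so the following are assumptions:

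- p = share low to pH1N1, 10% to 30%
- q = share low to the other virus, 10% to 30%
- r = correlation of log titres, 0 to 0.5, bivariate normal

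Share of the pH1N1-low stratum not low to the other virus = 1 − P(both low)/p.

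| p | q | r = 0 | r = 0.3 | r = 0.5 |
|---|---|---|---|---|
| 10% | 10% | 90% | 78% | 68% |
| 10% | 30% | 70% | 50% | 35% |
| 20% | 20% | 80% | 67% | 56% |
| 30% | 10% | 90% | 83% | 78% |
| 30% | 30% | 70% | 57% | 48% |

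Example, p = 10%, q = 30%, r = 0.5: P(both low) = 0.0653, and 1 − 0.0653/0.10 = 0.35.

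The range is about 35% to 90%. An effect confined to subjects low to the analysed virus would appear in G1a versus G2a at the complement, about 10% to 65% of its size.

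The reverse error is P(high to pH1N1 | low to the other virus) = 1 − P(both low)/q. For p = 10%, q = 30% it is 90%, 83% and 78% at r = 0, 0.3 and 0.5. Most H3-low subjects would then be analysed as seropositive.

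Wider assumptions widen the answer. With 10% to 50% low to pH1N1, 10% to 75% low to the other virus and r from 0 to 0.8, the not-low share runs from about 0% to 90%.

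**4. Would a two-group split be workable?** Section 12.2 plans 45 per group. If 10% were low, 45 × 0.10 = 4.5, so 4 or 5 per vaccine; at 30%, 45 × 0.30 = 13.5. The shares are assumed, but the Section 3.2 remark about scarce low-titre subjects points to small cells for pH1N1.

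**The case against.** **A reader might infer that the H3 and B comparisons are made largely in subjects who are not low to those viruses.** The documents do not support that. They give no baseline H3 or B titres. Inside the assumed range, at p = 10%, q = 30% and r = 0.5, 65% of the pH1N1-low stratum is low to the other virus. Only *not necessarily low* can be said.

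**A reader might infer that the comparison is biased.** For newly randomised subjects, G1a versus G2a on H3 remains a valid comparison within a subgroup defined at baseline. It answers a different question from the one the split was meant for.

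**Section 9.2.1 names only a pH1N1 antigen for HAI,** "using turkey RBCs and egg-grown, betapropiolactone-inactivated A/California/07/09 virus as antigen", and a pH1N1 reassortant for MN. Confining Section 12.4 to pH1N1 on that basis would contradict Section 4.2.1, so this objection does not remove the point.

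**Section 12.4 already deals with baseline elsewhere.** It correlates baseline CD4, HAI and MN values with boost responses, and its mixed models allow a difference-in-differences adjustment for baseline. This stands in part, and makes a flat conclusion that baseline is irrelevant less likely. But the correlations do not compare vaccines, and removing baseline level does not test whether the vaccine effect varies with it.

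**The split may be leftover text.** Sections 3.2 and 5 suggest so. That strengthens the case for revising Section 12.4, where the split still defines the named comparisons.

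**Conclusion.** The point holds as a matter of analysis definition. For H3 and B titres, and for CD4 pools other than H1, the Section 12.4 strata do not separate low from high prior immunity to what is being analysed. They therefore do not test the dependence that Section 1 gives as their purpose. This rests on reading Sections 12.4 and 4.2.1 together, and on the link between baseline titre and response in Section 3.1.

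The size is unknown. The 35% to 90% misclassified share depends wholly on the assumed prevalences, correlation and bivariate normal form.

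Two further points need no assumption. The low group of Section 1 is not the seronegative group of Section 12.4 as written. Both sections also keep a pH1N1 split whose screen Section 3.2 says was replaced, and which Section 5 no longer mentions.

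**What to change.** In Section 12.4:

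1. For each titre outcome, use the Day 0 titre to the virus being analysed. Preferably enter it as a continuous log2 covariate with a vaccine-by-baseline interaction, since few subjects may be at or below 1:8.
2. If a two-group split is kept, define it separately for each virus, with one stated cut-off and the label *low* in both Section 1 and Section 12.4.
3. Do not apply the pH1N1 split to non-H1 CD4 pools. Use the Day 0 response to the same pool as a continuous covariate, which avoids a cut-off that the plan does not have.
4. Reconcile Sections 1 and 12.4 with Sections 3.2 and 5, and include the vaccination-history stratum in the analysis.

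The Day 0 values are already needed for the change scores in Section 4.2.1, so no new samples or assays are required. The cost is revised wording, a little more analysis work and, if a split is kept, stratum sizes that differ by virus.

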3 BACKGROUND INFORMATION AND SCIENTIFIC RATIONALE

3.1 Background Information

Inactivated influenza vaccines (IIVs) have been in use in the US and worldwide for the prevention of illness due to seasonal and pandemic influenza since their licensure approximately 60 years ago. Multiple studies over many years have evaluated the immunogenicity of these vaccines in various populations. In general, serum antibody responses to IIV are vigorous in healthy young adults with low levels of pre-vaccination antibody. Nasal antibody responses can also be detected, although they are not as vigorous as those seen after live vaccination.

The serum antibody response to IIV is impacted by several factors, including the age of the subject, the presence of chronic diseases, and the use of immune modulating drugs. In addition, the prior exposure of the subject to influenza vaccine or infection appears to have a substantial impact on both the immune response as well as the protective efficacy of IIV. For seasonal influenza vaccine, the magnitude of the serum antibody response is lower in individuals who begin with higher prevaccination titers, and highest in those with low prevaccination titers. Consistent with this observation, individuals with prior vaccination, and who therefore have higher baseline antibody titers, tend to have less vigorous antibody responses to revaccination. The impact of prior vaccination on protection is controversial. Some studies have suggested that vaccine efficacy is higher in those who were not vaccinated in the previous season than in those who were [1, 2]. Other studies have not seen this association [3]. The mechanisms by which prior exposure to vaccine or infection might modify the subsequent response to IIV are not known, but would have obvious implications for the design of new influenza vaccines and vaccine strategies.

Growth of virus in embryonated hen's eggs has been used for production of IIV since these vaccines were first introduced. For the influenza A components of the vaccine, the selected reference antigenic variant for that season is typically reassorted with the high-yield laboratory influenza A/PR-8 virus to generate a seed virus that can replicate to high titer in eggs. In some cases, the seed virus may require additional passage in eggs to achieve adequate growth levels in this substrate. Harvested virions are subsequently concentrated, chemically inactivated, and disrupted with detergent, and the HA and NA proteins are partially purified by chromatography and other proprietary methods to yield a preparation referred to as split-product, subvirion, or subunit vaccine, depending on the manufacturer. In addition to containing a standardized amount of HA protein as determined by single radial immunodiffusion (SRID), licensed IIV preparations contain variable, but substantial amounts of NA as well as matrix (M) and

nucleoprotein (NP). Thus, it is possible that repeated exposure to the highly conserved NP and M proteins plays a role in the effect of prior vaccination on subsequent antibody responses.

Recently, two inactivated vaccines made from alternative substrates have been licensed in the US for seasonal use. These include mammalian cell culture grown inactivated vaccine (FluCelVax) [4] licensed for individuals ages 4 and above, and a purified recombinant baculovirus-expressed HA vaccine (FluBlok) made in insect cells [5] and licensed for ages 18 and above. Cell culture grown vaccine is made using a different type of seed virus and purification process which could result in a different mixture of proteins in the final preparation. In contrast, the baculovirus-expressed HA vaccine is a completely different preparation that contains over 95% pure HA protein without any other components of influenza virus. The availability of these additional licensed forms of influenza vaccine has provided an opportunity to evaluate the role that prior immunity to the various components of the vaccine plays in the antibody response, and to specifically address the hypothesis that CD4 recognition of epitopes specifically on the HA protein plays the major role in help for HA-specific B cell responses.

The basic composition of vaccines currently licensed in the US for seasonal influenza that are being used in this study are shown below:

Vaccine	Fluzone (SD)	Fluzone (HD)	Flublok	FluCelVax
Production	Eggs (avian)	Eggs (avian)	Sf9 cells (insect)	MDCK cells (mammalian)
Inactivation	Formaldehyde	Formaldehyde	NA	b prioprolactone
Disruption	Triton X-100	Triton X-100	NA	Cetyltrimethyl-ammonium bromide
Purification	Sucrose gradient, additional concentration	Sucrose gradient, additional concentration	Column chromatography	ND
Dose	15 ug/HA	60 ug/HA	45 ug/HA	15 ug/HA
Indication	6 mo, and older	65 yrs and older	18 yrs and older	4 yrs and older
Components [§]				
H1N1	A/Michigan/45/2015 X-275*	A/Michigan/45/2015 X-275*	A/Michigan/45/2015	A/Singapore/GP1908/2015 IVR-180**
H3N2	A/Hong Kong/4801/2014 X-263-B*	A/Hong Kong/4801/2014 X-263-B*	A/Hong Kong/4801/2014	A/Singapore/GP2050/2015
B Yamagata	B/Phuket/3073/2013	NA	B/Phuket/307/2013	B/Utah/9/2014
B Victoria	B/Brisbane/60/2008	B/Brisbane/60/2008	B/Brisbane/60/2008	B/Hong Kong/259/2010

Source: Individual 2017-2018 FDA package inserts

§ All virus components are antigenically consistent with current WHO recommendations, however egg-grown viruses may contain egg adaptation changes not contained in mammalian cell or baculovirus expressed vaccines

*X-275 and X-263-B represent reassortants with A/PR/8 (H1N1) for high yield growth in eggs, the HA and NA are derived from the vaccine viruses

**IVR-180 represents a reassortant with A/Texas/1/77 (H3N2) selected for high-yield growth in mammalian cell culture, the HA and NA are derived from the vaccine virus

[figure not shown]
NA – Not applicable. ND – Not described in the package insert

